#### **d. Analysis of Secondary Endpoints**

Time (in days) in between PRN treatments, change in respiratory inspiratory flow rate from baseline to discharge, length of stay, at-home drug compliance, 30-day readmissions (all-cause and COPD/Asthma exacerbation), and 30-day survival will be compared between patients who were and were not readmitted using t-tests or chi-square tests (or Wilcoxon Rank Sum tests and Fisher's Exact tests), as appropriate.

The efficacy of the treatment protocol in the study cohort compared to the historical cohort will be assessed by comparing (1) the average number of PRN treatments per patient day while hospitalized estimated using a robust Poisson regression model (2) length of stay in the hospital, and (3) the rate of rehospitalization, using the Wilcoxon Rank sum test.

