Safety Assessments:	

• Vital signs and vital status.

• Concomitant medication use.

• Reporting of adverse events.

• Pregnancy test (women of childbearing potential).

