#### **5.2.5 DISCHARGE**

Upon discharge, patients will receive a full TRELEGY ELLIPTA inhaler containing 30 doses with instructions to take 1 puff daily in the morning for 30 days. The in-hospital use TRELEGY ELLIPTA used by the patient will be discarded.

The following procedures/assessments will be done prior to hospital discharge:

- Spirometry (FEV1, FVC, FEV1/FVC)
- Peak inspiratory flow rate, measured by the InCheck Dial set at medium resistance.
- Concomitant Medications
- Adverse Events (AE) Assessment
- Patient Satisfaction Questionnaire (St George's Respiratory questionnaire, short version)

In addition, data from the specified assessments will be collected when available, and entered the case report forms (CRFS):

- Vital signs
- Withdrawal from protocol

If for any reason, some of the research assessments at discharge are not performed, the study team may (at investigator's discretion) schedule a follow-up with the subject in the research clinic to obtain the missed assessments.

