#### **5.2.6 30 DAY POST DISCHARGE/WITHDRAWAL FOLLOW-UP**

Subjects will receive a follow-up phone call from a study coordinator and Medical Charts will be reviewed to assess if the subject was readmitted within 30 days of discharge. Follow-up phone call and Medical Chart review will instead occur 30 days after withdrawal for patients who are withdrawn prior to discharge.

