### 7.2 Disallowed Medications

Subjects will be prohibited from taking the following medications during the study:

- Inhaled short-acting muscarinic antagonist (SAMAs), such as ipratropium bromide.
- Inhaled therapies other than TRELEGY ELLIPTA containing any of the following: ICS, LAMA, or LABA.

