## **9. STATISTICAL ANALYSIS & DATA MANAGEMENT**

Continuous variables will be reported as means  $\pm$  standard deviations or medians [quartile 1, quartile 3], if skewed. Categorical variables will be reported as frequencies and percentages.

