### **8.2. Measurement of Efficacy**

Efficacy will be assessed by the number of in-hospital PRN respiratory therapy treatments with PRN nebulized albuterol 2.5mg, time in between PRN respiratory therapy, change in respiratory inspiratory flow rate measured by InCheck DIAL at medium resistance from baseline to discharge, length of stay, at-home drug compliance, 30-day re-admissions (all-cause and COPD exacerbation), 30-day survival, cost of in-hospital respiratory therapy, and response to a patient satisfaction questionnaire (QOL questionnaire).

Drug compliance at home will be assessed through follow-up phone call at 30-day post-discharge. Compliance will be calculated as the difference between 100 and the percentage of doses left on the TRELEGY ELLIPTA inhaler out of 30.

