### **c. Analysis of Primary Endpoint**

The number of PRN respiratory treatments during hospitalization will be reported as the median [quartile 1, quartile 3] and as the average number of PRN respiratory treatments per inpatient day  $\pm$  standard deviation. A comparison between patients who were and were not readmitted within 30-days will be made using a Wilcoxon signed rank test for the number of PRN respiratory treatments. Additionally, the incident rate ratio of the average per-inpatient

day PRN treatments will be estimated using a robust Poisson regression model comparing patients who were readmitted within 30-days to those who were not.

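### Both 30-day readmission endpoints are tested between groups defined by readmission itself, and the same grouping biases the 30-day survival comparison in favour of readmitted patients

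*Combined protocol and SAP*

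**What the plan says.** Section 8.7 d (Analysis of Secondary Endpoints) lists several outcomes and ends with the statement that "30-day readmissions (all-cause and COPD/Asthma exacerbation), and 30-day survival will be compared between patients who were and were not readmitted". The tests named are t-tests or chi-square tests, with rank-sum or Fisher's exact tests as alternatives.

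The window of the grouping comes from Section 8.7 c, where "A comparison between patients who were and were not readmitted within 30-days will be made" for the PRN treatment counts. Section 5.2.6 ascertains readmission over the same period: "Medical Charts will be reviewed to assess if the subject was readmitted within 30 days of discharge". Neither part of Section 8.7 says whether the grouping is all-cause or COPD/asthma readmission.

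A separate paragraph of Section 8.7 d compares PRN treatments, length of stay and rehospitalization with the historical cohort. Survival is not in that paragraph, so the comparison by readmission status is the only one planned for it. Section 8.7 contains no landmark, no time-dependent readmission variable and no rule for patients who die before they could be readmitted.

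**The concern.** An outcome cannot be tested between groups that the outcome itself defines. The result is settled by the definition before any data are collected, and the p-value measures only how many patients fell in each group.

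The all-cause row will look odd in any table and may be caught. The COPD/asthma row is more dangerous: 20% vs 0% with p = 0.02 reads like an ordinary finding, although the zero is forced. Section 8.4 plans an abstract and a manuscript, so such a row could be published.

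Survival is a different problem. A patient must be alive to be readmitted, so every death before readmission falls in the not-readmitted group. Deaths during the index stay, if counted, fall there too. The readmitted group is thus credited with survival time that its members had to complete in order to enter it.

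**Working it through.** **Inputs from the documents.** Section 4 a: 120 approached × 2/3 accepting = 80 enrolled, which reproduces the enrollment figure. With 80% followed to day 30, 0.80 × 80 = 64. If chart review classifies everyone, N = 80. The plan gives no readmission rate, COPD/asthma share or death rate, so those below are assumptions.

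**1. All-cause endpoint, all-cause groups.** With n readmitted, the table is n/n vs 0/(N − n), and the Fisher p-value is 1/C(N, n).

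| N | readmitted | p |
|---|---|---|
| 64 | 10 | 6.6e-12 |
| 64 | 13 | 7.6e-14 |
| 64 | 16 | 2.0e-15 |
| 80 | 12 | 1.7e-14 |
| 80 | 16 | 3.7e-17 |
| 80 | 20 | 2.8e-19 |

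**2. COPD/asthma endpoint, all-cause groups.** With k COPD/asthma readmissions, the table is k/n vs 0/(N − n). In the cases below p = C(n, k)/C(N, k).

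- N = 64: 1/10, 10/64 = 0.16; 2/10, 45/2016 = 0.022; 2/16, 120/2016 = 0.060; 3/16, 560/41664 = 0.013.
- N = 80: 2/12, 66/3160 = 0.021; 3/20, 1140/82160 = 0.014.
- If half of 13 readmissions are for COPD/asthma (6/13 vs 0/51), p = 2.3e-5.

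A small p-value is not guaranteed, but two or three COPD/asthma readmissions can be enough.

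**3. COPD/asthma groups.** The COPD/asthma row becomes 100% vs 0%, and the all-cause row is forced to 100% in the readmitted group. With the same counts (6 COPD/asthma among 13 readmissions, N = 64), all-cause is 6/6 vs 7/58, again p = 2.3e-5. Neither choice of grouping rescues the tests.

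**4. Survival.** Take constant hazards over T = 30 days from discharge: a 5% death risk in the absence of readmission and a 20% readmission risk in the absence of death. Let HR be the true ratio of the death hazard after readmission to that before it.

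- λd·T = −ln 0.95 = 0.0513; λr·T = −ln 0.80 = 0.2231; s·T = 0.2744, where s = λd + λr.
- P(readmitted) = (λr/s)(1 − e^(−sT)) = 0.8131 × 0.24 = 0.1951.
- P(death, never readmitted) = (λd/s)(1 − e^(−sT)) = 0.1869 × 0.24 = 0.0449. Death risk among the not readmitted = 0.0449/0.8049 = 5.6%, whatever the HR.
- P(readmitted, then dead) = ∫ λr e^(−st)[1 − e^(−HR·λd(T − t))] dt from 0 to T. At HR = 1 this is 0.19514 − 0.95 × 0.20 = 0.00514, so the death risk among the readmitted is 0.00514/0.19514 = 2.6%.

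| True HR | deaths, not readmitted | deaths, readmitted | crude ratio (readmitted / not) | crude ratio / HR |
|---|---|---|---|---|
| 1 | 5.6% | 2.6% | 0.47 | 0.47 |
| 2 | 5.6% | 5.2% | 0.93 | 0.465 |
| 3 | 5.6% | 7.6% | 1.37 | 0.46 |

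The 5% is the risk before or without readmission. Total deaths are 5.0%, 5.5% and 6.0% in the three rows.

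Across 54 combinations (HR 0.5 to 5; death risk 2, 5 and 10%; readmission 10, 20 and 30%) the crude ratio was always below the true hazard ratio, at 0.40 to 0.51 of it.

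**The case against.** The strongest defence is that little harm follows. The all-cause row betrays itself once tabulated. With 3 to 10% deaths among 64 to 80 patients, only about 2 to 8 deaths are expected, so the survival test would say little even if unbiased. The 2/10 vs 0/54 example assumes that only a fifth of readmissions are for COPD/asthma; with a larger share the forced zero is easier to spot. All of this stands and limits the weight of the point. It does not give the tests a meaning. Nor can the sentence be shorthand for the historical comparison, which has its own paragraph.

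Two stronger readings are tempting.

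- A reader might infer that the grouping biases survival in an unknown direction, because readmitted patients may be sicker. Greater sickness is part of the association being measured, or confounding; it is not an effect of the grouping. The grouping always favours the readmitted. What cannot be foreseen is the sign of the observed difference.
- A reader might also infer that at-home compliance is distorted by the grouping, since Section 8.2 says "Compliance will be calculated as the difference between 100 and the percentage of doses left on the TRELEGY ELLIPTA inhaler out of 30" and a readmitted patient might not use the home inhaler. The documents do not say what is used during a readmission. Section 7.2 bars "Inhaled therapies other than TRELEGY ELLIPTA containing any of the following: ICS, LAMA, or LABA" during the study, and the institutional practice described in Section 3 c does not settle what study patients would receive. The argument is not established and supports no change.

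**Conclusion.** The point holds and should be fixed before analysis. The circularity of the two readmission tests follows from the text alone and needs no assumed rate; only the illustrative p-values depend on assumed counts. The survival bias also follows from the definition. Its size, about 0.45 to 0.47 of the true hazard ratio in the central case, rests on constant hazards and on assumed death and readmission rates. A true doubling of the death hazard would appear as 5.6% vs 5.2% in the opposite direction, so neither the size nor the sign of the observed difference can be interpreted.

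The reach is limited. PRN counts in Section 8.7 c are recorded during the index stay and are not circular with later readmission. The primary objective and the historical comparison of rehospitalization are unaffected by this point.

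**What to change.** In Section 8.7 d:

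- Delete both readmission endpoints and 30-day survival from the comparison by readmission status.
- State whether all-cause or COPD/asthma readmission defines the groups for the in-hospital variables that remain (time between PRN treatments, change in inspiratory flow, length of stay). Restrict that comparison to patients discharged alive with known 30-day status, so that patients never at risk of readmission are not counted as not readmitted.
- Report each type of 30-day readmission among patients discharged alive with known status, and 30-day survival among all patients with known vital status, as whole-cohort proportions with exact 95% confidence intervals. For example, 13/64 = 20% (11 to 32%) or 16/80 = 20% (12 to 30%). Give the number with known status, because Section 5.2.6 names only readmission for the day-30 contact.
- Keep the historical-cohort comparison of rehospitalization, and leave the compliance analysis as planned.
- If survival by readmission is still wanted, treat readmission as time-dependent or use a landmark.

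The cost is a short written amendment under Section 16.1 and the loss of p-values that carry no information. Section 9 already plans that "Categorical variables will be reported as frequencies and percentages", so the new analysis elements are the intervals and the stated denominators.

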## 2. OBJECTIVES & ENDPOINTS

### a. Primary Objective

1. To establish the requirements for PRN respiratory therapy treatments in patients hospitalized with the diagnosis of COPD exacerbation receiving once-daily ICS/LABA/LAMA (fluticasone furoate/umeclidinium/vilanterol) therapy.

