### b. Secondary Objectives

1. To measure the distribution of inspiratory flow rates with an InCheck Dial device set on measuring PIF using the medium low resistance setting in patients admitted with COPD exacerbations at Baylor University Medical Center, Dallas TX at the time of enrollment and day of discharge.
2. To determine the hospital length of stay for patients admitted with the diagnosis of COPD exacerbation.
3. To monitor and report any side effects from using once-daily ICS/LABA/LAMA or PRN therapy.
4. To evaluate the transition of care in delivering respiratory therapy medications from hospital to home.
5. To compare the number of PRN treatments, length of hospital stay, and rate of readmissions with findings in a previously analyzed historical cohort of 60 patients in our healthcare system.

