### d. Study Endpoints

To attain these objectives, the following study endpoints will be evaluated. Primary and secondary endpoints include the number of in-hospital PRN respiratory therapy treatments, time in between PRN respiratory therapy, change in peak inspiratory flow rate from baseline to discharge, length of stay, at-home drug compliance, 30-day re-admissions (all-cause and respiratory), 30-day survival, cost of respiratory therapy, QOL score, and safety measures (AEs and SAEs; Section 5). See section 8.7 on analytical methods to evaluate these endpoints.

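### Section 8.7 plans no interval for the cohort PRN rate, no inference on within-patient PIFR change and no QOL analysis; apart from a historical contrast, its inference is by later readmission status

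*Combined protocol and SAP*

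**What the plan says.** The primary objective (section 2.a) is a one-cohort estimation aim: "To establish the requirements for PRN respiratory therapy treatments in patients hospitalized with the diagnosis of COPD exacerbation" while receiving the once-daily inhaler. Secondary objective 1 (section 2.b) is "To measure the distribution of inspiratory flow rates with an InCheck Dial device", with measurements "at the time of enrollment and day of discharge". Section 8.2 counts change in inspiratory flow and the QOL questionnaire among the efficacy measures. Section 2.d lists PIFR change and QOL score as endpoints and directs the reader onward: "See section 8.7 on analytical methods to evaluate these endpoints".

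Section 8.7.c begins: "The number of PRN respiratory treatments during hospitalization will be reported as the median" with quartiles, and then "as the average number of PRN respiratory treatments per inpatient day" with a standard deviation. This follows the general descriptive rule that opens the statistics section. The rest of 8.7.c compares readmitted with non-readmitted patients, by a Wilcoxon test on the count and a robust Poisson rate ratio.

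In section 8.7.d, time between PRN treatments, PIFR change, length of stay and the other named endpoints "will be compared between patients who were and were not readmitted using t-tests or chi-square tests" or their nonparametric counterparts. A second paragraph compares the study cohort with the historical cohort on PRN treatments per patient day, length of stay and rehospitalization.

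**The concern.** A median with quartiles, or a mean with an SD, describes how patients differ from one another. It does not state how well the cohort value has been estimated, and estimating that value is the primary aim. No section commits to an interval for it.

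Readmission becomes known only after the in-hospital endpoints have been observed. Comparing PRN use or PIFR change by readmission status asks which in-hospital features go with later readmission. That is a reasonable exploratory question, but it is not how much PRN treatment patients need, nor whether flow or quality of life changed during the stay. If the plan is followed as written, most of the reported p-values and the 8.7.c rate ratio will answer a question that no objective poses. The PRN requirement, the PIFR change and the QOL change would have no planned inference within the treated cohort.

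**Working it through.** **1. What is planned for each endpoint (general descriptive rule, 8.7.c, 8.7.d)**

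| Endpoint | Whole treated cohort | Readmitted vs not | Study vs historical |
|---|---|---|---|
| PRN treatments | Median [quartiles]; mean per inpatient day ± SD | Wilcoxon test; robust Poisson rate ratio | Robust Poisson |
| Time between PRN treatments | General descriptive rule only | t-test or rank sum | None |
| PIFR change | General descriptive rule only | t-test or rank sum | None |
| Length of stay | General descriptive rule only | t-test or rank sum | Rank sum |
| QOL score | General descriptive rule at most | None | None |

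The whole-cohort column contains no interval and no paired analysis. The signed rank test named in 8.7.c does not fill the gap: it is a paired or one-sample test, but the text applies it to two independent groups. That is a separate matter.

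**2. The plan's own figures**

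Section 4.a: 120 × 2/3 = 80 enrolled, which agrees with the target in 8.7.b, and 80 × 0.80 = 64 with 30-day follow-up. Section 8.7.b gives no alpha, power, SD or precision target, so there is nothing further to reproduce.

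**3. Precision of a whole-cohort mean**

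Half-width of a 95% interval = 1.96 × SD/√n.

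- n = 80: 1.96/√80 = 0.219 SD.
- n = 64: 1.96/√64 = 0.245 SD.

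With t quantiles these become 0.223 and 0.250 SD. The same formula serves a patient-level mean of PRN treatments per day and a mean within-patient change. As an example with an assumed mean of 2.0 per day and SD of 1.5, at n = 80: 2.0 ± 0.219 × 1.5 = 1.67 to 2.33. A distribution-free interval for the median at n = 80 runs from the 31st to the 50th ordered value (96.7% coverage).

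For PIFR and QOL, n is the number of patients with both values. Eighty is then a best case, and 64 is only an illustrative smaller number.

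**4. Precision of the readmission contrast**

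Half-width = 1.96 × SD × √(1/n1 + 1/n2). The documents give no readmission share, so 10% to 30% is assumed.

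- n = 64, 10% (6 vs 58): 1.96 × √(1/6 + 1/58) = 0.84 SD.
- n = 64, 30% (19 vs 45): 1.96 × √(1/19 + 1/45) = 0.54 SD.
- n = 80, 10% (8 vs 72): 1.96 × √(1/8 + 1/72) = 0.73 SD.
- n = 80, 30% (24 vs 56): 1.96 × √(1/24 + 1/56) = 0.48 SD.

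Steps 3 and 4 concern different estimands. They show how loosely the planned contrast would be estimated and how tightly the cohort value could be. They are not the efficiency of two methods for one question.

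**5. The InCheck setting**

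Resistance is given as medium low in objective 1 (2.b), inclusion criterion f (4.b), the screening assessments (5.2.2) and 8.7.a. It is given as medium in the synopsis efficacy list, the discharge assessments (5.2.5) and 8.2. Read literally, a baseline-to-discharge change could mix two settings.

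**The case against.** The best defence is that the gap is one of reporting. Section 8.7.c already gives a mean per inpatient day with its SD, and 8.7.e fixes n as the patients with data, so a reader can form mean ± 1.96 SD/√n. This stands. A reader might infer that the trial could not say how precisely PRN need was established; the documents do not support that. The interval is obtainable but not committed to. It would also belong to the mean of patient-level rates, which can differ from total treatments divided by total days, and the plan does not say which is meant.

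The wording on PIFR also limits the point. Change from baseline is itself a within-patient difference, and the general rule would summarise it. Objective 1 asks only for a distribution, which descriptive statistics serve. What is missing is inference on a quantity that 8.2 calls an efficacy measure.

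The historical contrast is real inference on PRN rate, length of stay and rehospitalization, and it is not split by readmission. But it is relative, and it covers neither PIFR nor QOL.

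Three further inferences should be resisted:

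- **The split discards a fifth of patients with complete in-hospital data.** Chart review supplements the phone call (5.2.6), so readmission status may be known for more than 80%. In-hospital data are not guaranteed complete: PRN data are collected when available (5.2.4) and discharge assessments may be missed (5.2.5).
- **The ratio of the half-widths measures lost efficiency.** It does not, because the estimands differ.
- **Adjusting the readmission contrast for baseline PIFR would bring a calculable precision gain.** The usual formula assumes groups with equal expected baselines. These groups are not randomised and are formed after discharge.

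**Conclusion.** The point holds in a limited form, and the plan should be changed. Section 8.7 states no interval for the cohort PRN rate, which is the primary aim. It plans no inference on within-patient PIFR change, and neither 8.7.c nor 8.7.d analyses QOL, although 2.d and 8.7.a list it as an endpoint. Apart from the relative historical contrast, the planned inference concerns later readmission.

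This conclusion rests on the text alone. The illustrative precision in the working depends on the assumed readmission shares and, for PIFR and QOL, on how many patients have both values. The documents do not support saying that precision is unknowable or that PIFR change would go undescribed.

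**What to change.** - **8.7.c:** report PRN treatments per inpatient day in all treated patients with a 95% interval, from a robust Poisson model with log inpatient days as offset or a patient-level bootstrap. State whether the target is the pooled rate or the mean of patient rates.
- **8.7.d:** for all patients with both values, report the within-patient change in PIFR and in the St George's score with 95% intervals, with a paired t or Wilcoxon signed rank analysis. State the number of pairs.
- **8.7.c and 8.7.d:** label the readmission contrasts exploratory.
- **Before PIFR change is interpreted:** reconcile the InCheck setting across the sections listed in the working, and establish which setting was used at each measurement.

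The cost is SAP wording and a little extra analysis. PRN counts and times (5.2.4), PIFR (5.2.2 and 5.2.5) and the questionnaire (5.2.3 and 5.2.5) are already scheduled, so no new assessment is needed.

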Results of an analysis of 60 patient charts randomly selected after hospitalization at Baylor University Medical Center for an exacerbation of underlying airways disease (>90% with COPD) showed tremendous variation in practice patterns; with 30% of patients receiving short-acting beta-antagonists and muscarinic agonists (SABA/SAMA) only, 70% receiving long-acting beta-antagonists (LABA) with PRN SABA/SAMA, and only 42% receiving a long-acting muscarinic agonist (LAMA), despite practice guidelines encouraging the use of SABA/SAMA only (typically 4 times daily and as needed).

It is this large variability that renders the evaluation and interpretation of institution-specific outcomes difficult. The main impetus for the proposed study is therefore to establish a more standardized open-label protocol which would allow for a more accurate assessment of intervention outcomes. As one of several secondary goals of this study, we aim to compare key outcomes (including, number of PRN treatments, length of hospital stay, and rate of readmission) with those from the historical cohort described above, when a combination LABA/LAMA/ICS inhaler is used as the primary scheduled daily inhaled therapy.

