#### 4. PATIENT POPULATION

**a. Enrollment Goal**

This study aims to enroll 80 subjects. With an anticipated acceptance rate of 2/3, this means we will approach 120 eligible candidates over that period. We estimate we will be able to achieve 30-day follow-up in 80% of enrolled patients.

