**ii. Exclusion Criteria**

- a. Clinically significant lung disease other than COPD with or without asthma.
- b. Positive SARS-CoV-2 test at the time of ED or hospital admission, or any time between admission and enrollment.
- c. History of severe hypersensitivity to milk proteins or demonstrated hypersensitivity to fluticasone furoate, umeclidinium, vilanterol, or any of the excipients.
- d. Unable to perform inspiratory flow or spirometry procedures.
- e. Critically ill patients, or patients with rapidly deteriorating or life-threatening episodes of COPD or asthma including:
  - Patients in critical care unit, or transferred from critical care unit.

- Patients who are transferred to critical care after enrollment will be withdrawn from the study and continue to receive care according to institutional standard practice.
- Patients who initiate Bilevel Positive Airway Pressure (BiPAP) after hospitalization.
  - Patients who use BiPAP at baseline (prior to COPD exacerbation) may be included if BiPAP settings remain consistent with pre-exacerbation settings. Patients will be withdrawn if BiPAP settings are changed after enrollment.

f. Pregnant or lactating women or women of child-bearing potential (WOCBP). Women must meet the non-productive potential definition below to be eligible.

➤ Non-reproductive potential is defined as:

- Pre-menopausal females with one of the following:
  - Documented tubal ligation.
  - Documented hysteroscopic tubal occlusion procedure with follow-up confirmation of bilateral tubal ligation.
  - Hysterectomy.
  - Documented Bilateral Oophorectomy.
- Postmenopausal defined as 12 months of spontaneous amenorrhea with an appropriate clinical profile (e.g., age appropriate, >45 years, in the absence of hormone replacement therapy). In questionable cases for women <60 years of age, a blood sample with simultaneous follicle stimulating hormone and estradiol falling into the central laboratory's postmenopausal reference range is confirmatory. Females under 60 years of age, who are on HRT and whose menopausal status is in doubt, are required to use a highly effective method to avoid pregnancy if they wish to continue their HRT during the study. Otherwise, they must discontinue HRT to allow confirmation of postmenopausal status prior to study enrolment. For most forms of HRT, at

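### Section 8.7.d assesses efficacy against 60 unrestricted historical charts, without adjustment or a stated common counting start, so a difference cannot be attributed to the treatment protocol

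*Combined protocol and SAP*

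**What the plan says.** Secondary objective 5 (section 2.b) compares PRN treatments, length of stay and readmissions with a previously "analyzed historical cohort of 60 patients in our healthcare system". Section 8.7.d introduces the analysis with "The efficacy of the treatment protocol in the study cohort compared to the historical cohort will be assessed by comparing" three outcomes. The first, PRN treatments per patient day, gets a robust Poisson model with no covariates named. The others are "2) length of stay in the hospital, and (3) the rate of rehospitalization, using the Wilcoxon Rank sum test".

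The two cohorts are formed differently:

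- **Charts (section 3.c).** They are "60 patient charts randomly selected after hospitalization at Baylor University Medical Center for an exacerbation of underlying airways disease (>90% with COPD"). No exclusions, calendar period or counting window are given.
- **Study, at entry (section 4.b).** Patients need an inspiratory flow of at least 30 L/min. Critical care, BiPAP started after hospitalization and a positive SARS-CoV-2 test are exclusions.
- **Study, after entry.** "Patients who are transferred to critical care after enrollment will be withdrawn from the study", and "Patients will be withdrawn if BiPAP settings are changed after enrollment". Section 6.4 adds withdrawal for a later positive SARS-CoV-2 test.
- **Study, data window.** The number and time of SABA treatments are listed in section 5.2.4, which runs from enrollment to discharge. Enrollment may be up to 24 hours after admission (sections 4.b.i and 5.2.3).
- **Study, readmission.** Section 5.2.6 uses a phone call and chart review at 30 days after discharge, but at 30 days after withdrawal for patients withdrawn before discharge. Section 4.a adds: "We estimate we will be able to achieve 30-day follow-up in 80% of enrolled patients".

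**The concern.** This is the plan's only comparison between treatment approaches. The other tests in sections 8.7.c and 8.7.d split study patients by readmission status. The cohorts differ in who may enter, who is taken out after deteriorating, and possibly in the hospital day from which PRN use is counted. Random selection makes the charts representative of past admissions. It does not make them comparable with patients who met the study criteria. A per-day rate corrects for how long patients were observed, not for which days were observed.

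Section 3.c gives variable practice as the reason why local outcomes are hard to interpret, and presents the study as a way to assess them more accurately. Results are intended for publication (sections 8.4 and 17). At stake is a published efficacy statement that reflects case mix and counting as much as treatment.

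**Working it through.** **Figures in the documents.** 120 approached × 2/3 = 80 enrolled, which reproduces the target. It is accrual arithmetic only; no alpha, power, effect size or SD is given. 80% of 80 = 64 with 30-day follow-up. More than 90% of 60 means at least 55 charts with COPD, so at most 5 without.

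The rest is illustration. It assumes no true treatment effect, takes one mechanism at a time, and uses inputs that are not in the documents.

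**1. Counting start.** Let L be the stay in days, k the first-day PRN rate relative to later days, and d the lag in days from admission to the start of study counting (at most 1). If the charts count from admission:

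ratio = {[(1 − d)k + L − 1]/(L − d)} ÷ {(k + L − 1)/L}

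- d = 1, so ratio = L/(k + L − 1). L = 3, k = 2: 3/4 = 0.75. L = 5, k = 2: 5/6 = 0.83. k = 1: 1.00.
- d = 0.5, L = 3, k = 2: (3/2.5)/(4/3) = 1.20/1.33 = 0.90.
- d = 0 (same start in both cohorts): 1.00.

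With L from 3 to 5 and k from 1 to 2, the one-day lag gives 0.75 to 1.00. A k below 1 would put the ratio above 1.

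**2. Eligibility.** If a share q of charts fail the study criteria and stayed m times as long, the length-of-stay ratio is 1/[1 + q(m − 1)].

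- q = 0.10, m = 1.5: 1/1.05 = 0.95.
- q = 0.20, m = 2: 1/1.20 = 0.83.

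**3. Remaining in hospital until enrollment.** Suppose a share s of charts left after one day, before they could have been enrolled, and the rest averaged L days. The length-of-stay ratio is then L/[s + (1 − s)L].

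- s = 0.10, L = 3: 3/2.8 = 1.07.
- s = 0.20, L = 5: 5/4.2 = 1.19.

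This runs against mechanism 2, so the net direction is open.

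**4. Scale against random error.** With patient-level coefficient of variation CV, SE(log PRN ratio) = CV × √(1/80 + 1/60).

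- CV = 0.7: SE 0.120, 95% CI factor exp(1.96 × 0.120) = 1.26.
- CV = 1.0: SE 0.171, factor 1.40.

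The chance that a nominal two-sided 5% test rejects is Φ(|ln ratio|/SE − 1.96) + Φ(−|ln ratio|/SE − 1.96).

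- Ratio 0.75: 39% (CV 1.0) to 67% (CV 0.7).
- Ratio 0.90: 9% to 14%.

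**5. Readmission precision.** At an assumed 20% rate in both cohorts, the half-width is 1.96 × √[0.16 × (1/64 + 1/60)] = 14.1 percentage points.

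**The case against.** The comparison is one of several secondary goals, with no alpha or success rule. Section 8.2 uses the word efficacy for every outcome, including cost and questionnaire response. The rank sum test is valid for length of stay, and on a yes/no outcome it behaves much like a two-proportion test. Any adjusted analysis would still leave unmeasured severity and calendar time. All of this stands, and it limits how much the point matters. It does not supply the missing restriction, counting start or covariates, and section 8.7.d applies the word efficacy specifically to a contrast between treatment approaches.

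Several stronger readings are tempting but not supported:

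- **Scheduled doses were counted as PRN in the charts.** A reader might infer this from "despite practice guidelines encouraging the use of SABA/SAMA only (typically 4 times daily and as needed"). That phrase describes guidance, not abstraction. The same sentence reports PRN SABA/SAMA as a category of its own. How the charts were counted is not stated, so no size can be attached.
- **The bias favours the study drug.** Mechanism 3 shows that it need not.
- **Study PRN data exist only from enrollment.** This is an inference from a section heading. Treatment times are recorded, so a common start can be applied from enrollment onward.
- **Length of stay is shortened by counting from enrollment.** Section 8.7.d refers to stay in the hospital, which gives no basis for this.
- **Readmission is unknown in 16 of 80 patients.** Section 5.2.6 includes chart review as well as the call, and section 4.a does not say which the 80% refers to.

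It would also be wrong to infer that the primary summary is untouched. Section 8.7.c reports PRN treatments per inpatient day, and the same question about the counting start applies to it.

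**Conclusion.** The concern holds. As written, section 8.7.d yields an unadjusted comparison of a restricted cohort, with withdrawals for deterioration, against charts with no stated restriction. A difference cannot be attributed to the treatment protocol. Confidence is high that the restriction, common start and covariates are absent; it is not high for any particular size of bias.

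The 0.75 end of the PRN range needs the maximum one-day lag, a three-day stay and first-day use twice later use. A half-day lag with the same inputs gives 0.90, and matched windows give 1.00. For readmission, two questions are unresolved: whether withdrawn patients enter the comparison, and whether their 30 days can be aligned with those of patients followed from discharge. The point should be addressed before analysis, but it concerns a secondary objective and does not invalidate the study.

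**What to change.** In section 8.7.d:

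1. Restrict the charts to patients who meet the study criteria that can be verified from a chart and who are still hospitalized at a comparable time after admission. Keep withdrawn study patients in the comparison where consent allows. State that inspiratory flow and willingness to consent cannot be matched.
2. Count PRN treatments and patient-days from the same start in both cohorts, with one PRN definition for both. State the start point for the primary per-inpatient-day figure in section 8.7.c as well.
3. Adjust the PRN, length-of-stay and readmission comparisons for a few baseline variables available in both cohorts, for example age and sex, plus severity if charted. Report readmission as a difference in proportions with a confidence interval.
4. Measure readmission over 30 days from discharge by chart review in both cohorts, and report the number ascertained.
5. Describe the comparison as exploratory rather than as efficacy.

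**Cost.** No new patients are needed. The work is SAP wording, re-review of up to 60 charts, and chart review of withdrawn patients to 30 days after discharge. If 12 charts drop out (60 to 48) and CV = 1.0, SE = √(1/80 + 1/48) = 0.183 and the PRN CI factor goes from 1.40 to 1.43. The readmission half-width goes from 14.1 to 1.96 × √[0.16 × (1/64 + 1/48)] = 15.0 points. Unmeasured severity and calendar-time differences remain. The documents do not show whether re-abstraction is feasible. If it is not, item 5 alone is the minimum change and costs one sentence.
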